8.3.3 Evaluation of Specific Antibody Response Against Recall Antigens in Serum

To determine whether SBRT affects humoral immune responses, serum samples will be analyzed for IgG anti-tetanus toxoid antibody. Briefly, antibodies against pooled peptides of tetanus toxoid will be used to capture specific IgG anti-tetanus toxoid antibodies in participant serum, followed by detection of bound antibodies using goat-anti-human IgG by enzyme linked immunosorbent type assay (ELISA). In addition, we will also test the T and B cell responses to pokeweed mitogen in a polyclonal T-dependent in vitro B cell antibody synthesis assay. The IgG antibody titers to tetanus toxoid at different time points after radiation will be compared to baseline measurements.

8.3.4 Evaluation of IFN-y secreting T cells specific to tumor using an EliSpot assay

To determine whether SBRT affects the tumor specific cytotoxic T cells, PBMC will be isolated from whole heparinized blood by Ficoll-hypaque density gradient centrifugation and cryopreserved until use. PBMC will be exposed to a cocktail of stimulating tumor cells (either lung cancer cell lines-A549, H292 and H520 or liver cancer cell lines-SK-HEP-1, SNU-423 and SNU-475) in plates coated with anti-human IFN- γ antibody. The interferon gamma (IFN- γ) EliSpot assay measures the CD8-mediated cytotoxic T lymphocyte (CTL) activity and CD4-mediated helper responses. IFN- γ EliSpots produced by PBMC will be assessed after 18 hours of stimulation with the above listed cocktail of cell lines as well as spontaneous IFN- γ EliSpots (non-stimulated PBMC) produced by PBMC at an effector to target ratio (E/T) of 1:1. This will allow for detection of tumor specific IFN- γ cytokine producing activated T cells. The quantification of IFN- γ secreting specific T cells will be performed by EliSpot CTL software.

The results of the lymphocyte functionality *in vitro* analyses will be compared between Arms A and B and correlated to integral or mean great vessel radiation dose, mean heart dose, and mean lung dose.

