3.3 Exploratory Objectives

3.3.1 Lymphocyte Phenotype and Function (additional)

Determine the phenotype and function of lymphocytes in vitro in Arm A versus Arm B patients.

Endpoint: Specific anti-tumor interferon gamma (IFN-γ) EliSpot responses to lung cancer cell lines.

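### The EliSpot in section 8.3.4 cannot separate tumour-specific T-cell responses from alloreactive or NK responses, so the tumour-specific label on this exploratory endpoint is not supported

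*Combined protocol and SAP*

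**What the plan says.** Section 8.3.4 describes the assay as follows.

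- **Responders:** "PBMC will be isolated from whole heparinized blood by Ficoll-hypaque density gradient centrifugation and cryopreserved until use". No T-cell selection or NK depletion is described.
- **Stimulators:** "PBMC will be exposed to a cocktail of stimulating tumor cells (either lung cancer cell lines-A549, H292 and H520 or liver cancer" lines, of which three are then named. These are established lines, not the participant's own tumour. HLA typing or matching is not mentioned.
- **Read-out:** spots "will be assessed after 18 hours of stimulation with the above listed cocktail of cell lines".
- **Comparator:** spontaneous spots only, described in the words "non-stimulated PBMC) produced by PBMC at an effector to target ratio (E/T) of 1:1".

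The section states that the "EliSpot assay measures the CD8-mediated cytotoxic T lymphocyte (CTL) activity and CD4-mediated helper responses", and says of the result: "This will allow for detection of tumor specific" T cells producing IFN-γ. In section 3.3.1 and in Synopsis Table 1 the exploratory endpoint is worded "Specific anti-tumor interferon gamma" EliSpot responses, and both name lung cancer lines only.

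On analysis, section 8.3.4 says that the in vitro results "will be compared between Arms A and B and correlated to integral or mean great vessel radiation dose, mean heart dose, and mean lung dose". It names no model.

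**The concern.** A tumour-specific claim needs a condition that shows the spots come from T cells recognising tumour antigen. Unfractionated PBMC also contain NK cells, and lines from other people may present foreign HLA. Either can yield IFN-γ spots above the spontaneous background.

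The trial's own premise raises the stakes. The Introduction says that lymphocyte subsets differ in radiosensitivity. An arm difference in spots could therefore reflect a change in the make-up of the PBMC or in general reactivity. Under the current wording it would be reported as better preserved anti-tumour immunity after lymphocyte-sparing planning, which the data could not show.

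A second, smaller issue is that the analysis is left open. Each participant's HLA relation to the lines does not depend on treatment. It can add between-patient variation to a comparison of about 25 evaluable participants per arm, and the text does not commit to using the pre-SBRT value to reduce it.

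**Working it through.** **1. What the subtraction identifies.** The documents give no spot counts, variances or cell-type shares, so there is no stated figure to reproduce. Write the expected stimulated count as S and the spontaneous count as U. Then

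S − U = A + N + T,

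where A is alloreactive T-cell spots, N is NK spots and T is tumour-specific T-cell spots. The design gives one quantity for three unknowns. T/(A + N + T) can take any value from 0 to 1.

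**2. Whether anything in the plan separates the terms.**

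| Possible separator | In the plan? |
|---|---|
| Autologous or HLA-matched tumour targets | Not described |
| Non-malignant allogeneic cells as control | Not described |
| HLA blocking | Not described |
| T-cell selection or NK depletion | Not described |
| Defined tumour-antigen peptides | Not described |
| Second tumour type run in parallel | No; the liver lines are an either/or alternative to the lung lines |
| NK share measured by flow cytometry | Section 8.3.2 names T-cell, monocyte and MDSC markers but no NK marker |
| Further assays | Section 8.3 permits them but commits to no specificity control |

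**3. What the arm contrast still estimates.** Randomisation makes the arm difference in S − U a valid contrast of the sum A + N + T. That is overall IFN-γ reactivity to the lines, not T alone.

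**4. What is stated about the analysis.** Section 8.3.3 states a comparison with baseline for tetanus IgG. Section 8.3.4 states none for EliSpot. The repeated-measures model in section 5 is for lymphocyte counts. The baseline value will nevertheless exist: section 8.3.1 runs the functional assays at each draw, and section 8.2 and the calendar in section 9 place research draws before SBRT and at about 4 weeks.

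**5. What a baseline covariate buys.** With pre/post correlation r, equal variances and a linear relation, the residual variance after adjustment is (1 − r²) of the unadjusted variance. The values of r are assumptions; the documents give none.

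- r = 0.5: 1 − 0.25 = 0.75
- r = 0.7: 1 − 0.49 = 0.51
- r = 0.8: 1 − 0.64 = 0.36

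**6. What it does not buy.** If the correlation arises from a constant patient effect, that effect makes up a share r of the variance. One noisy baseline removes only r²:

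- r = 0.5: 25% removed of a 50% patient share
- r = 0.7: 49% of 70%
- r = 0.8: 64% of 80%

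Adjustment reduces the patient effect but does not remove it. The effect is also constant only if the same cocktail is used at both draws, which the either/or wording does not ensure.

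**The case against.** The strongest defence is that this is one exploratory endpoint in a pilot, with no alpha, power or decision rule attached. The endpoint text already discloses that the stimulus is a set of lung cancer cell lines. Section 8.3.4 opens by asking whether SBRT affects these cells, which implies a before-and-after reading. The randomised contrast stays interpretable as overall reactivity. All of this stands and lowers the severity, but none of it makes the read-out specific.

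Three stronger readings are tempting and should not be drawn.

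- **That the assay mainly reads alloreactive and NK responses.** This is a statement of magnitude. No figure in the documents supports it, and it contradicts the fact that the shares are not identifiable.
- **That the arm comparison is planned as unadjusted.** The text is silent on the model, so it is unspecified. Likewise, HLA matching is not mentioned, which is not a statement that none will be done.
- **That HLA mismatch could bias the comparison.** Randomisation rules out systematic imbalance, and a valid standard error already reflects chance imbalance. What remains is lost precision, of a size the documents do not give.

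**Conclusion.** The point holds in a limited form. The design described cannot distinguish tumour-specific T-cell responses from alloreactive or NK responses, so the specificity wording in section 8.3.4, section 3.3.1 and Table 1 is not supported. This rests on the assay as written and on the general understanding that unfractionated PBMC can respond to such lines in more than one way. It does not rest on any assumed share.

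The precision gain of 25%, 49% or 64% in residual variance depends entirely on the assumed correlations. The endpoint is exploratory, and the primary lymphocyte-count aims and the sample size do not depend on it. Severity is minor.

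**What to change.** 1. In Synopsis Table 1, section 3.3.1 and section 8.3.4 (including its heading), rename the endpoint as the IFN-γ response of PBMC to established lung cancer cell lines. Delete the claim that it detects tumour-specific T cells, and state that the result is read as overall cellular reactivity.
2. Reconcile the liver-line option in section 8.3.4 with the lung-only endpoint in Table 1 and section 3.3.1. State that the same cocktail is used at both draws.
3. In section 8.3.4, specify the outcome as stimulated minus spontaneous spots at 4 weeks, with the pre-SBRT value of the same quantity as covariate, for both the arm comparison and the dose correlations.

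The cost is wording and one covariate already collected, with no new assay and no extra blood. The price is a narrower claim. If the sponsor wants to keep the specificity claim, it would have to add a specificity control of the kind listed in the table above, which would mean additional laboratory work.

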9. STUDY CALENDAR OF ASSESSMENTS

Procedures	Screening/Baseline ¹	SBRT (5 clinic days)	Completion of SBRT ⁵	4 weeks +/-2 weeks following SBRT	3 months +/-2 weeks following SBRT	6 to 9 months following SBRT	Overall Survival (every 6 months for one year and then annually, by phone or medical record review)
Informed consent	X						
Demographics	Х						
Medical history	Х						
Randomization	X^7						
Concomitant medication review	X8		X			X	
Physical exam	Х		Х		Х		
COVID-19 Questions	Х		Х		Х	Χ	
Vital signs	Х		Х		Х		
Height	X (last recorded for standard clinical care)						
Weight	Х		X ⁶			X ⁶	
Performance status	X		X			Х	
Serum or urine pregnancy test (Women of Childbearing Potential Only)	Х						
0 110 1 1 (00)							
Overall Survival (OS)							Х
Hematology- CBC with Diff	X		X ⁴	Х		Х	X ³
Research Blood	X ²			Х			
Planning/Chest CT	X (w/in 8						
scan with contrast	wks of SBRT) ⁷				X ⁶		
Review of Medical Record (see section 8.1.4)	Х		Х		Х	Х	Х
Adverse event review and evaluation	X					X	
SBRT		Х					

¹ All screening procedures should occur up to 1 month prior to registration unless otherwise specified

10. DATA AND SAFETY MONITORING PLAN

10.1.1 DSMC Meetings and Audits

The UVA CC DSMC will meet every month for aggregate review of data. Tracking reports of the meetings are available to the PI for review. Issues of immediate concern by the DSMC are brought to the attention of the sponsor (and if appropriate to the PRC and IRB) and a formal

29

²Research blood should be completed following confirmation of eligibility/registration and before beginning SBRT.

³ If the participant is followed at UVA and CBC results are available in Epic, these should be entered in the designated EDC system (q 6 months +/- 1 month).

4 Complete within 3 days after completion of SBRT (can be immediately following completion of SBRT)

⁵ Complete within 5 business days (before or after) of completion of SBRT unless otherwise stated

⁶Only collected if part of standard clinical care. Not collecting this information during/following SBRT is not considered a deviation Registration and randomization should occur around the time of planning CT (+/- 5 business days). SBRT must begin within 4

weeks after registration/randomization. ⁸ Medications should be collected from 28 calendar days before registration

response from the sponsor is requested. Per the UVA Cancer Center NIH approved institutional plan, this study will be audited approximately every year. The audit may include direct access to source data/documents.

10.2 Adverse Events and Serious Adverse Events

10.2.1 Definition of Adverse Events (AE)

Adverse event means any untoward medical occurrence associated (at least possibly related) with the use of a medical intervention in humans.

10.2.2 Definition of Serious Adverse Events (SAE)

An adverse event (AE) or suspected adverse reaction is considered "serious" if, in the view of either the investigator or sponsor, it results in any of the following outcomes:

- death,
- a life-threatening adverse event,
- inpatient hospitalization or prolongation of existing hospitalization,
- a persistent or significant incapacity or substantial disruption of the ability to conduct normal life functions, or
- a congenital anomaly/birth defect.

Important medical events that may not result in death, be life-threatening, or require hospitalization may be considered serious when, based upon appropriate medical judgment, they may jeopardize the participant and may require medical or surgical intervention to prevent one of the outcomes listed in this definition. Examples of such medical events include allergic bronchospasm requiring intensive treatment in an emergency room or at home, blood dyscrasias or convulsions that do not result in inpatient hospitalization, or the development of drug dependency or drug abuse.

A planned medical or surgical procedure is not, in itself, an SAE.

10.2.3 Classification of an Adverse Event

10.2.3.1 Severity of Event

For adverse events (AEs) not included in CTCAE version 5, the following guidelines will be used to describe severity.

- **Mild** Events require minimal or no treatment and do not interfere with the participant's daily activities.
- **Moderate** Events result in a low level of inconvenience or concern with the therapeutic measures. Moderate events may cause some interference with functioning.
- **Severe** Events interrupt a participant's usual daily activity and may require systemic drug therapy or other treatment. Severe events are usually potentially life-threatening or incapacitating. Of note, the term "severe" does not necessarily equate to "serious".

10.2.3.2 Relationship to Study Intervention

All adverse events (AEs) must have their relationship to study intervention (both SBRT and blood draws that are completed solely for the research study) assessed by the clinician who examines and evaluates the participant based on temporal relationship and his/her clinical judgment. The degree of certainty about causality will be graded using the categories below. In a clinical trial, the study product must always be suspect.

- Definitely Related There is clear evidence to suggest a causal relationship, and other
 possible contributing factors can be ruled out. The clinical event, including an abnormal
 laboratory test result, occurs in a plausible time relationship to study intervention
 administration and cannot be explained by concurrent disease or other drugs or
 chemicals. The response to withdrawal of the study intervention (dechallenge) should be
 clinically plausible. The event must be pharmacologically or phenomenologically definitive,
 with use of a satisfactory rechallenge procedure if necessary.
- Probably Related There is evidence to suggest a causal relationship, and the influence
 of other factors is unlikely. The clinical event, including an abnormal laboratory test result,
 occurs within a reasonable time after administration of the study intervention, is unlikely
 to be attributed to concurrent disease or other drugs or chemicals, and follows a clinically
 reasonable response on withdrawal (dechallenge). Rechallenge information is not
 required to fulfill this definition.
- Possibly Related There is some evidence to suggest a causal relationship (e.g., the
 event occurred within a reasonable time after administration of the trial medication).
 However, other factors may have contributed to the event (e.g., the participant's clinical
 condition, other concomitant events). Although an AE may rate only as "possibly related"
 soon after discovery, it can be flagged as requiring more information and later be upgraded
 to "probably related" or "definitely related", as appropriate.
- **Unlikely to be related** A clinical event, including an abnormal laboratory test result, whose temporal relationship to study intervention administration makes a causal relationship improbable (e.g., the event did not occur within a reasonable time after administration of the study intervention) and in which other drugs or chemicals or underlying disease provides plausible explanations (e.g., the participant's clinical condition, other concomitant treatments).
- **Not Related** The AE is completely independent of study intervention administration, and/or evidence exists that the event is definitely related to another etiology. There must be an alternative, definitive etiology documented by the clinician

10.2.3.3 Expectedness

The treating clinician will be responsible for determining whether an adverse event (AE) is expected or unexpected. An AE will be considered unexpected if the nature, severity, or frequency of the event is not consistent with the risk information previously described for the study intervention.

The following side effects are considered expected from a standard blood draw, in order of likelihood: pain, bruising, fainting or passing out, or infection. SBRT radiation side effects should be consistent with standard clinical care. The likely SAEs from SBRT are described in Bezjak et al from RTOG 0813, which included patients receiving SBRT radiation for centrally located NSCLC¹⁵. In addition to these SAEs from SBRT, participants may experience a drop in lymphocyte count, lung fibrosis, fatigue and/or skin irritation/skin changes.

10.2.4 Time Period and Frequency for Event Assessment and Follow-Up

The occurrence of an adverse event (AE) or serious adverse event (SAE) may come to the attention of study personnel during study visits and interviews of a study participant presenting for medical care, or upon review by a study monitor.

All reportable AEs including local and systemic reactions not meeting the criteria for SAEs will be captured on the appropriate case report form (CRF). Information to be collected includes event description, time of onset, clinician's assessment of severity, relationship to study product (assessed only by those with the training and authority to make a diagnosis), and time of resolution/stabilization of the event. All AEs occurring while on study must be documented appropriately regardless of relationship. All AEs will be followed to adequate resolution.

Any medical condition (including a laboratory abnormality) that is present at the time that the participant is screened will be considered as baseline and not reported as an AE. However, if the study participant's condition deteriorates at any time during the study, it will be recorded as an AE. For the purposes of this study, laboratory abnormalities (at baseline or during the study) will not be recorded and are not reportable, except for hematological laboratory abnormalities in a complete blood count (with or without differential), as these are the only laboratory results that have any likelihood of being related to SBRT/study intervention.

Changes in the severity of an AE will be documented to allow an assessment of the duration of the event at each level of severity to be performed. AEs characterized as intermittent require documentation of onset and duration of each episode.

Study staff will record all reportable events with start dates occurring any time after informed consent is obtained until the 6 month visit following SBRT (for non-serious AEs) or anytime (for SAEs considered related to the study intervention). At each study visit, the investigator will inquire about the occurrence of AE/SAEs since the last visit. Events will be followed for outcome information until resolution or stabilization.

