6.1 Patient Registration & Randomization

All participants must sign the consent form prior to determination of eligibility for this study. Patients will be screened and evaluated to meet all eligibility criteria before being registered on the trial. Once a patient is determined to be eligible for the study, study staff will register the patient in the UVA Cancer Center OnCore database in accordance with the Clinical Trial Management System Policy, via the UVA OnCore Resources link in Oncore. Participants will be associated with a UVA unique identifier, such as UVA SBRT-001, that will represent the participant in the study. This will be listed as the participant's sequence number in the OnCore database and will be on all research blood samples collected from participants.

Randomization will be discussed with participants during the process of informed consent and informed consent must be documented prior to randomization. Participants will be randomized 1:1 to Arm A or Arm B using randomly permuted blocks, with block sizes of 2 or 4 randomly chosen with equal probability. Stratification is described below. Randomization will be performed using custom randomization software (RAND) that incorporates the randomization scheme generated by the study statistician. Clinical research staff and treating clinicians will be aware of arm assignment and participants may be made aware of their arm assignment. The labels on research blood will not include the treatment arm on which the participant is assigned and this information will not be provided to lab investigators and staff.

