10.2.5 Adverse Event Reporting

AEs considered related to either a research-only blood draw or SBRT must be recorded into the University of Virginia Cancer Center's designated EDC database in accordance with the Clinical Trial Management System Policy Note that the AE Reporting Table below has been revised in the following ways from the standard AE Reporting table for Low Risk Studies:

- Reporting for grade 4-5 unrelated AEs was updated to "Not Required" because this study includes participants that may have severe/serious AEs due to their disease that are completely unrelated to SBRT or blood draws. All treatment meets standard of care guidelines.
- Reporting for Grade 1-2 (expected and unexpected) was updated to "30 days", as investigators are interested in reviewing ALL related AEs for feasibility/equivalence of safety.
- Reporting for laboratory AEs is limited to complete blood count (with or without differential), as these are the only laboratory adverse events that would have any possibility of relationship with SBRT

Table C: Low Risk Studies

Reporting requirements for AEs that occur within 6 months of the last protocol specified treatment/intervention					
	Grade 1-2	Grade 1-2 Unexpected		Grade 3	Grade 4-5
	Expected			Expected or Unexpected	Expected or Unexpected
		Without hospitalization	With hospitalization	·	·
Unrelated	Not required	Not required	Not required	Not required	Not required
Related	30 days**	30 days**	30 days**	15 days**	(24-hrs)* 15 days**

^{*}Enter into Cancer Center database within 24 hours if unexpected and definitely related to protocol specified treatment Hospitalization defined as an inpatient hospital stay or prolongation of a hospital stay equal to or greater than 24 hours ** The only laboratory AEs that need to be reported are hematological studies, as SBRT will not affect other laboratory results

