10.2.6 Serious Adverse Event Reporting

The study clinician will record any serious adverse event, whether or not considered study intervention related, including those listed in the protocol, and must include an assessment of whether there is a reasonable possibility that the study intervention caused the event.

All serious adverse events (SAEs) will be followed until satisfactory resolution or until the site investigator deems the event to be chronic or the participant is stable.

- Internal Events Resulting in death that are deemed DEFINITELY related to (caused by) study participation
 - Report to the UVA IRB-HSR within 24 hours. Report within 24 hours using IRB Online and a phone call.
- Internal, Serious, Unexpected, Related to Study Intervention
 - Report to the UVA IRB-HSR within 7 days from the time the study team receives knowledge of the event. Timeline includes submission of signed hardcopy of AE form. Report using IRB Online.

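### The AE rules conflict on whether relatedness is required and on when capture ends, leaving the descriptive by-arm safety table open to filtering by clinicians who know the arm

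*Combined protocol and SAP*

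**What the plan says.** **Which events count.** Section 10.2.1: "Adverse event means any untoward medical occurrence associated (at least possibly related) with the use of a medical intervention in humans". Section 10.2.3.2 nevertheless has the clinician grade relationship on a scale that includes *Unlikely to be related* and *Not Related*. Section 10.2.4: "All AEs occurring while on study must be documented appropriately regardless of relationship". The same section limits the CRF: "All reportable AEs including local and systemic reactions not meeting the criteria for SAEs will be captured on the appropriate case report form (CRF". Section 10.2.5: "AEs considered related to either a research-only blood draw or SBRT must be recorded" into the designated EDC database. Table C marks unrelated events of every grade as *Not required*. For serious events, Section 10.2.6 states: "The study clinician will record any serious adverse event, whether or not considered study intervention related".

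**When capture ends.** Section 10.2.4 records events "until the 6 month visit following SBRT (for non-serious AEs"; SAEs considered related are recorded at any time. The study calendar (Section 9) places that visit at 6 to 9 months after SBRT. Table C is headed "Reporting requirements for AEs that occur within 6 months of the last protocol specified treatment/intervention".

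**Who judges.** Section 10.2.3.2 gives attribution to the clinician who examines the participant. Section 6.1: "Clinical research staff and treating clinicians will be aware of arm assignment".

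**What the data are for.** Section 3.2.1 is a secondary objective describing the AE profile in both arms. Its hypothesis is that the profiles are similar, apart from fewer or milder lymphocyte decreases in Arm A. Section 5 will tabulate AEs and estimate differences between groups as an exploratory analysis, without a test or margin.

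**The concern.** Two teams following this protocol in good faith could build different safety datasets. One would hold everything documented under Section 10.2.4 plus all SAEs under Section 10.2.6. The other would hold only events called related.

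The choice matters because randomization protects a comparison of all events by arm. It does not protect a comparison of events that first pass a judgement made with knowledge of the arm. An unforeseen excess in the investigational arm would show in the unfiltered count but could be lost if each event is first screened by opinion. Section 11.1.4 asks the monitoring committee to review all adverse events; under the Section 10.2.1 definition that set is already filtered. Section 10.2.5 also gives equivalence of safety as a reason for collecting AEs, which raises the importance of how events are selected.

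**Working it through.** The plan gives no AE rate, margin or safety power, so there is no figure to reproduce. The check has two parts: follow test events through the rules, then illustrate size with assumed rates.

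**1. Test events against each rule**

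| Event | 10.2.1 | 10.2.4 | 10.2.5 and Table C | 10.2.6 |
|---|---|---|---|---|
| (a) Grade 2, judged unlikely related, month 2 | Not an AE | Documented; on the CRF only if reportable | Entry not required | Does not apply |
| (b) Grade 4 with hospitalization, judged not related, month 2 | Not an AE | Documented | Not required | Recorded |
| (c) Grade 2, related, onset month 7, visit at month 8 | AE | Captured | Outside 6 months | Does not apply |
| (d) Grade 2, related, onset month 7, visit at month 6 | AE | Not captured | Outside 6 months | Does not apply |

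Events (a) and (b) get different answers depending on the section followed. Event (b) is sharper because Section 10.2.2 defines a serious event as a kind of AE or suspected adverse reaction; under Section 10.2.1 an unrelated SAE hardly exists, yet Section 10.2.6 requires it. Events (c) and (d) are clinically identical and differ only in when the visit was scheduled.

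**2. Filtering by attribution (assumed rates)**

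Recorded risk = true risk × probability of being called related.

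- Equal true risk of 40%, with 80% versus 60% called related: 0.40 × 0.80 = 0.32 and 0.40 × 0.60 = 0.24. The spurious difference is 8 points, ratio 0.32/0.24 = 1.33.
- Smallest unequal case examined (true risk 20%, 80% versus 70%): 0.16 − 0.14 = 2 points.
- Largest case examined (true risk 60%, 80% versus 50%): 0.48 − 0.30 = 18 points.
- Equal attribution at any true risk: 0 points.

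For scale, the 95% half-width for 32% versus 24% at 25 per arm is 1.96 × √(0.32×0.68/25 + 0.24×0.76/25) = 24.8 points. Across the cases examined it is about 19 to 28 points. Section 5 counts anyone who starts SBRT as evaluable for AEs, so the true denominators may be somewhat above 25 and the intervals somewhat narrower.

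**3. The end of capture (assumed constant hazard, counted from the last fraction)**

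Risk by 9 months = 1 − (1 − risk by 6 months)^(9/6). A 6-month risk of 20% becomes 1 − 0.8^1.5 = 28.4%. This is a difference between participants with different visit dates. Between arms, it matters only if visit timing differs. With mean visits at 7 versus 8 months, the spurious difference at a 20% 6-month risk is 0.8^(7/6) − 0.8^(8/6) = 2.8 points (1.5 to 4.9 points for 6-month risks of 10% to 60%). With the same timing in both arms it is zero.

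**The case against.** The strongest defence is that Section 10.2.4 separates *documented* from *reportable*: everything goes into source notes, and only reportable (related) events go to the CRF and database. Table C can likewise be read as a schedule of reporting deadlines that does not cancel the recording of SAEs. Section 10.2.5 also gives a reason for not reporting unrelated grade 4-5 events, namely that such events are expected from the underlying disease. This reading reconciles much of Sections 10.2.4 and 10.2.5. It does not reconcile the Section 10.2.1 definition with the *Not Related* grade, or the different end dates. It also confirms that unrelated non-serious events need not reach the dataset that will be tabulated.

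The second defence is that attribution is to SBRT or a research blood draw, and both arms receive SBRT at the same prescribed range. The question put to the clinician is not whether the optimized plan caused the event, and the threshold is only possible relatedness. That stands: attribution may well be similar between arms, and nothing in the documents supports any particular pair of attribution rates. What remains is that knowledge of the arm can still influence a judgement that decides whether an event is counted.

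The third defence is that the safety comparison is descriptive, and in the illustrations with 25 per arm the sampling error exceeds the assumed distortions. That also stands, and it limits the consequence.

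**Conclusion.** The conflict is in the current text and should be reconciled. As written, the by-arm AE description can rest on events selected by clinicians who know the arm. The direction and size of any bias cannot be determined from the documents. The 2 to 18 points above depend entirely on assumed rates, and the bias is zero if attribution is equal between arms. The 6-to-9-month visit window is common to both arms, so it is mainly an inconsistency and a source of noise. Primary conclusions are not affected.

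Three stronger readings are tempting, but the documents do not support them.

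- *That the hypothesized lymphocyte difference could arise from attribution alone.* Lymphocyte counts are measured by scheduled CBC in both arms and compared directly in the primary analysis with no attribution step. Section 10.2.3.3 also lists a lymphocyte drop among the effects participants may experience. Only the entry of such a drop as an AE passes through attribution.
- *That a participant seen at 9 months has AE capture 50% longer than one seen at 6.* Section 10.2.4 starts capture at consent, so the ratio is (9 + c)/(6 + c), where c is the months from consent to the end of SBRT. With c assumed at 1 to 2 months this is 10/7 = 1.43 to 11/8 = 1.38.
- *That Section 10.2.4 already requires all AEs to be tabulated.* It requires documentation; CRF capture is limited to reportable events.

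**What to change.** 1. Reconcile Sections 10.2.1, 10.2.4, 10.2.5 with Table C, and 10.2.6 to one rule: all AEs enter the dataset and are tabulated by arm, with relatedness recorded as an attribute and related events shown as a subset. Expedited reporting deadlines can stay limited to related events, provided the text says that they govern reporting and not entry. Cost: protocol wording and modest extra data entry for events that clinicians already document.

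2. Derive CTCAE grades for lymphocyte count decreased directly from the scheduled CBC values in both arms, with no attribution step. Tabulate these by scheduled visit, since a strict day cut would drop final CBCs drawn between 6 and 9 months. Cost: none beyond programming; the values are already collected.

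3. Cut the AE tabulation at 6 months after the last fraction for every participant, using the onset times that Section 10.2.4 already collects, and state the same end point in Section 10.2.4 and Table C. The calendar visit falls at or after 6 months, so everyone who attends it is covered to the cut-off. Later events can be listed separately. Cost: none in data collection.
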